10.4 Planned analyses

The main statistical analysis is planned when the planned number of patients have been included and have finalized data collection. Furthermore all data has to be entered, verified and validated according to the data management plan.

Prior to the main statistical analysis, the data base will be locked for further entering or altering of data. A separate statistical analysis plan (SAP) will provide further details on the planned statistical analyses. The SAP will be finalized, signed and dated prior to database lock. The treatment allocation will be revealed after the database lock and used in the statistical analysis. There will be no interim analysis.

Deviation from the original statistical plan will be described and justified in the Clinical Study Report. Amendments to plan can be done until day of DB lock.

10.5 Statistical Analysis

10.5.1 Primary analysis and Secondary analysis

The linear mixed-model procedure will be used to compare the effect of different treatments in the NRS in the cold-pressor pain model. This is a variance component model that takes into account correlations/dependence as a result of repeated treatments, carryover effects, and repeated observations in each treatment session on each subject. This statistical analysis is appropriate for a crossover study with repeated measurements.

The dependent variables were changes from baseline in the NRS in the cold-pressor pain model. For all analyses, pairwise comparisons between the treatments will be made only if the overall test for the difference between all treatments was significant at the level of 0.05. This Fisher's least significant difference method provides protection for multiple comparisons. Data will be analyzed in SPSS.

The primary endpoint is NRS during CPR at time zero

The secondary endpoint is NRS during CPR at time 15 min

Statistical hypothesis test:

- Null hypothesis: The difference in pain between the treatment (metoxyflurane) is at least 0.5 point on the 0-10 NRS scale in favor of the control treatment (fentanyl 0.05 mg).
- Alternative hypothesis: The difference in pain between the treatment (metoxyflurane) is less than 0.5 point on the 0-10 NRS scale in favor of the control treatment (fentanyl 0.025 mg).

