6.2.1 Before Treatment Starts

- Evaluating patient eligibility: The subjects should be in good health and not have any chronic illness. Both sex will be included. The subject will be recruited from the general population.
- Assessing baseline values of parameters used as end-points: Each session starts with a CPT (time -15 minutes), see flow-chart 6.1. The NRS values from the first CPT are the baseline values the end-points will be evaluated from in each session.

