6.4 Procedures for Discontinuation

6.4.1 Patient Discontinuation

Subject who gets any kind of severe adverse effects will be followed up.

All patients randomized will be included in the study population.

Patients who withdraw or are withdrawn from the study after randomisation cannot be replaced.

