7 ASSESSMENTS

7.1 Assessment of Response

The following parameters of response will be recorded:

Pain scores (NRS):

The subjects will undergo CPT (cold pressor test) to determine the analgesic effect of the drugs.(13,14) The CPT will be conducted using a temperature-controlled bath with circulating 3°C water (FP 45-HE Refrigerated/Heating Circulator, Julabo Labortechnik, 77960 Seelback, Germany). The subjects submerge their right hand to the wrist with fingers abducted for up to 90 s. The endpoints are NRS scores every 10 s. This test will be performed 3 times for each session.

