10 STATISTICAL METHODS AND DATA ANALYSIS

10.1 Determination of Sample Size

The power analysis is based on data from one of our previous study using the same model, the cold pressor test.(13)

This is a crossover study. Data on standard deviation of differences between the conditions in a paired comparison is used in the calculation. nQuery Advisor software was used to calculate the sample size and to do the power analysis" A sample size of 10 will have 80% power to detect a difference in means of 0,500 (e.g. a First condition mean, of 6,000 and a Second condition mean of 5,500), assuming a standard deviation of differences of 0,500, using a paired t-test with a 0,050 two-sided significance level . We will include 12 subjects to achieve a more exact block-randomization.

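### Section 10.5.1 analyses change from each session's pre-drug CPT and names no baseline covariate; adding that covariate is a cheap likely gain in precision, not the repair of an error

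*Combined protocol and SAP*

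**What the plan says.** Section 10.5.1 plans a linear mixed model comparing the four treatments. On the outcome it says: "The dependent variables were changes from baseline in the NRS in the cold-pressor pain model". The model is said to allow for dependence arising from repeated treatments, "carryover effects, and repeated observations in each treatment session on each subject". No covariate is mentioned.

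The baseline belongs to the session, not only to the subject. Section 6.2.1 states: "The NRS values from the first CPT are the baseline values the end-points will be evaluated from in each session". It is therefore measured four times per volunteer. Section 7.1 adds: "The endpoints are NRS scores every 10 s", with immersion lasting at most 90 s.

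The sample size in section 10.1 comes from a paired t-test: "Data on standard deviation of differences between the conditions in a paired comparison is used in the calculation". It does not say whether those differences are between raw NRS scores or between changes from baseline. The step from 10 to 12 subjects is not an allowance for dropout: "We will include 12 subjects to achieve a more exact block-randomization". Section 6.4.1 adds: "Patients who withdraw or are withdrawn from the study after randomisation cannot be replaced".

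Section 10.4 leaves room for more detail: "A separate statistical analysis plan (SAP) will provide further details on the planned statistical analyses". That SAP is not among the documents. The same section allows amendments to the plan up to database lock.

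**The concern.** A change score is often used to remove stable differences between people. In this crossover each volunteer is their own control, so that work is already done. What the session baseline can still explain is day-to-day variation within a person, such as a more sensitive day. Plain subtraction assumes that this variation passes one-for-one from the pre-drug to the post-drug CPT. If it carries over only in part, subtraction adds the noise of the baseline reading to every treatment comparison.

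Precision is what is at stake. There are 12 volunteers, none can be replaced, and section 10.3 bases the primary analysis on those without major protocol violations. The difference of interest is 0.5 NRS points, so the width of the interval decides how much the trial can say about equipotency.

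**Working it through.** **1. The plan's own figure.** Inputs from section 10.1: difference 0.5, SD of differences 0.5, two-sided alpha 0.05, paired t-test. Exact noncentral-t power is 74.8% at n = 9, 80.3% at n = 10 and 88.3% at n = 12. The stated n = 10 is correct for its inputs.

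**2. Variance of a treatment contrast.** Let r be the within-subject, session-level correlation between baseline and post-drug NRS, and let k = baseline SD / post-drug SD. In units of the post-drug variance:
- change score: 1 + k² − 2rk, which is 2(1 − r) when k = 1
- with the baseline covariate: (1 − r²) × (1 + 1/(df − 2)), where the last factor is the price of estimating the slope

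I assume subject, period and treatment effects and one complete value per CPT. Then df = 48 − 12 − 3 − 3 = 30 at n = 12, and 40 − 10 − 3 − 3 = 24 at n = 10. The price factor is 1 + 1/28 = 1.036 and 1 + 1/22 = 1.045 respectively.

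**3. Equal SDs (k = 1), n = 12.** r is not in the documents, so a range is shown.

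| r | change: 2(1 − r) | covariate: 1.036(1 − r²) | SE ratio, change / covariate |
|---|---|---|---|
| 0 | 2.00 | 1.036 | 1.39 |
| 0.25 | 1.50 | 0.971 | 1.24 |
| 0.5 | 1.00 | 0.777 | 1.13 |
| 0.75 | 0.50 | 0.453 | 1.05 |
| 0.9 | 0.20 | 0.197 | 1.01 |

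Setting the two variances equal gives break-even r = 2/(1 + 1/(df − 2)) − 1, which is 0.93 at n = 12 and 0.91 at n = 10. In simulation, first-order carryover terms (27 df) leave the excess almost unchanged: 38%, 24%, 13%, 5% and 1%. A separate REML simulation of the 12 × 4 crossover gave empirical SEs, covariate v change, of 0.131 v 0.147 at r = 0.5, 0.142 v 0.143 at r = 0.9 and 0.148 v 0.148 at r = 0.95.

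**4. Unequal SDs, n = 12.** The best slope is r/k, so change scores do best when r is close to k.
- k = 0.75: the change-score SE is 23% larger at r = 0 and 2% larger at r = 0.5. There is no gain from about r = 0.60 to 0.85, and a gain of about 4% returns at r = 0.9.
- k = 1.25: the change-score SE is 23% to 57% larger over r = 0 to 0.9.

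**5. Worst-case loss.** When the best slope is exactly 1, the covariate model pays only the price factor: √1.036 = 1.0177 (1.7–1.8% in SE) at n = 12 and √1.045 = 1.022 (2.2%) at n = 10.

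**6. Power for a 0.5 difference, n = 12, equal SDs.** These figures use pooled mixed-model df (30, or 29 with the covariate) and depend on the unstated scale of the SD of 0.5.
- If it refers to raw NRS, the SD of differences in change is 0.5√(2(1 − r)). Power, change v covariate, is 66% v 91% at r = 0, 78% v 92% at r = 0.25 and 92% v 97% at r = 0.5.
- If it refers to change scores, power without the covariate is 92% at every r (88% by the paired t-test). With it, power is about 99.6%, 99%, 97%, 94% and 92% at r = 0, 0.25, 0.5, 0.75 and 0.9.

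Both sets assume complete data and balanced sequences, and they ignore the overall test that section 10.5.1 requires before pairwise comparisons.

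**7. How the covariate enters.** A single uncentred baseline term mixes between-subject and within-subject slopes. At r = 0.2, with an assumed between-subject correlation of 0.95, the simulated SE was 0.144 for change alone, 0.126 with one uncentred term and 0.110 with the within-subject deviation plus the subject mean. Session baseline plus subject mean is the same model as the last.

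**The case against.** The strongest reply is that nothing here is wrong. Change from a pre-drug baseline is unbiased under randomisation, the sample size is right for its inputs, and the SAP may already include the covariate. All of that stands. The documents show only that section 10.5.1 does not mention a covariate, not that the SAP lacks or excludes one.

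A second reply is that the benefit depends on an r that the documents do not give. That also stands: at r = 0.9 with equal SDs almost nothing is gained. The case rests on the imbalance between a possible gain of up to 39% in SE with equal SDs and a loss capped at about 2%.

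A reader might infer three stronger points that the documents do not support.
- *A universal cut-off near r = 0.9.* It holds only for equal SDs. With k = 0.75 the no-gain range is about 0.60 to 0.85.
- *An underpowered trial.* Power falls below 80% at n = 12 only if the SD of 0.5 is on raw NRS and r is low. If it is on the change scale, no planned power is lost.
- *An inflated type I error because the 10-second readings are treated as independent.* Section 10.5.1 says that the model accounts for repeated observations within a session, so that fault belongs to an analysis that the plan does not propose.

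**Conclusion.** The point holds as an efficiency improvement. With equal SDs, complete data and 12 subjects, change scores cost about 39% in SE at r = 0, 13% at r = 0.5 and 1% at r = 0.9, compared with the same data and the baseline as covariate. At r = 0.5 the variance falls by about 22% (1 − 0.777). No single value of r separates gain from no gain, because the answer also depends on the ratio of the two SDs. The size of the benefit is therefore uncertain, while the downside is small and known. The change is worth making, with moderate confidence that it will matter.

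**What to change.** In section 10.5.1, or in the SAP before database lock:
- Keep the planned mixed model with its repeated-observation and carryover structure, and add two covariates: the session's pre-drug CPT NRS and the subject's mean pre-drug NRS.
- Either analyse one prespecified summary per CPT (for example the mean of the 10-second readings), defined identically for baseline and outcome, or keep all readings and include a subject-by-session random effect.
- State how readings are handled when the hand is withdrawn before 90 s, at baseline as well as after the drug. If all readings are kept, state whether the baseline is matched by time point or is a CPT summary.

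The outcome may stay as change from baseline. Subtracting a term that is also in the model only shifts that term's coefficient by 1, so treatment estimates and their SEs are identical to those for post-drug NRS.

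The cost is a few sentences, about 1 of 30 residual df, and an SE at most about 2% larger if subtraction happens to be optimal. No new data are needed.

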There exists no exact data of equipotent doses between metoxyflurane and fentanyl, only retrospective clinical data. One retrospective study compared intranasal fentanyl with inhaled metoxyflurane for visceral pain prehospital in 1024 patients.(10) The initial dose of fentanyl was 0.018 mg and the total mean dose at hospital arrival was 0.036 mg. In the metoxyflurane group 51.9% received 3 ml, a second dose was used in 41.9% and 6.2% received a third dose. Metoxyflurane produced the greatest initial pain scores reduction, and intranasal fentanyl provided greater pain reduction by hospital arrival.

From these data we have chosen two doses of fentanyl to be compared with 3 ml Pentrox: 0.025 mg and 0.05 mg intravenous. Both drugs will also be compared to placebo (NaCl 9 mg/ml).

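### Section 10.5.1 sets its null and alternative against different fentanyl doses and bounds the difference on one side only, so the plan has no rule that can establish equipotency, its only stated aim

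*Combined protocol and SAP*

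**What the plan says.** The synopsis and sections 1.1, 1.3 and 2 all give one aim: to determine equipotent doses of inhaled methoxyflurane and intravenous fentanyl. Section 1.3 makes both fentanyl doses comparators: "we have chosen two doses of fentanyl to be compared with 3 ml Pentrox: 0.025 mg and 0.05 mg intravenous".

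Section 10.5.1 then states one pair of hypotheses. Under the null, the difference "is at least 0.5 point on the 0-10 NRS scale in favor of the control treatment (fentanyl 0.05 mg". Under the alternative, it "is less than 0.5 point on the 0-10 NRS scale in favor of the control treatment (fentanyl 0.025 mg".

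The analysis described in the same section is a linear mixed model on change from baseline NRS, with a gate: "pairwise comparisons between the treatments will be made only if the overall test for the difference between all treatments was significant" at 0.05 (Fisher's LSD). Section 10.1 bases the sample size on detecting a 0.5-point difference, "using a paired t-test with a 0,050 two-sided significance level".

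On later detail, section 10.4 says: "A separate statistical analysis plan (SAP) will provide further details on the planned statistical analyses". It adds: "The SAP will be finalized, signed and dated prior to database lock".

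**The concern.** There are two separate faults in the hypotheses, and the analysis does not make up for either.

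- **Different comparators.** A null and its alternative should divide the possibilities for one quantity. Here the null concerns methoxyflurane against 0.05 mg and the alternative concerns methoxyflurane against 0.025 mg. Section 10.5.1 does not say which comparison counts, and section 1.3 wants both.
- **A bound in one direction.** Both statements limit only how far fentanyl may be better. Nothing limits how far methoxyflurane may be better. That is the form of a non-inferiority claim, whereas equipotency needs a limit on both sides.
- **A margin that is never used.** The overall test and the LSD comparisons ask whether treatments differ. Neither is set against 0.5, and no confidence-interval rule is given.

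At stake is whether the trial can state a conclusion on its own aim under a rule fixed in advance.

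**Working it through.** Let D be the true mean NRS difference, methoxyflurane minus fentanyl, so that positive values favour fentanyl.

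**Inputs.** From 10.1: difference 0.5, SD of paired differences 0.5, two-sided alpha 0.05, 10 subjects needed, 12 to be included. From 10.5.1: margin 0.5. Not in the documents, so assumed: one-sided alpha for a margin test (0.05 and 0.025 both shown), SDs of 0.75 and 1.0, and a pooled mixed-model error with (12 − 1) × (4 − 1) = 33 df as a stand-in beside the paired t with 11 df.

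**1. The plan's own figure.** Paired t power comes from the noncentral t with noncentrality (0.5/0.5) × √n and n − 1 df. It gives 74.8% at n = 9, 80.3% at n = 10 and 88.3% at n = 12. The stated 10 reproduces. It is the power to detect a difference.

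**2. Can both hypotheses be true?** Suppose methoxyflurane equals 0.025 mg and 0.05 mg is 0.5 points better. Against 0.025 mg, D = 0, which is below 0.5, so the alternative is true. Against 0.05 mg, D = 0.5, which is at least 0.5, so the null is also true. The pair is not complementary.

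**3. What meeting the alternative would show, with one dose named in both.** Test D < 0.5 one-sided at 0.025 with n = 12. The standard error is 0.5/√12 = 0.144, the critical value is t(0.975; 11 df) = 2.201, and the noncentrality is (0.5 − D)/0.144. The comparison is with two one-sided tests (TOST) at ±0.5.

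| True D | Noncentrality | Written alternative met | TOST passes (one-sided 0.025 / 0.05) |
|---|---|---|---|
| 0 | 3.46 | 88.3% | 76.6% / 88.9% |
| −0.5 | 6.93 | over 99.9% | 2.5% / 5.0% |
| −1.0 | 10.39 | about 100% | about 0% / about 0% |

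**4. What the written procedure would do.** A two-sided 0.05 pairwise comparison at a true difference of 0.5 is significant 88% of the time (11 df) or 92% (33 df), provided the overall test has been passed. It would usually flag a difference of that size. It contains no step that can affirm its absence.

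**5. Power if the bound is made two-sided.** TOST power averages Φ((h − D)/se) − Φ((−h − D)/se) over the sampling distribution of the estimated SD. Here se is the true standard error, and h = 0.5 − t(1 − α) × the estimated standard error, counted only where h > 0. For one comparison with D = 0 and SD 0.5:

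| Completers | Paired, 0.05 / 0.025 | Pooled, 0.05 / 0.025 |
|---|---|---|
| 12 | 88.9% / 76.6% | 91.9% / 83.9% |
| 10 | 79.5% / 61.4% | 84.9% / 72.3% |

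At one-sided 0.05 and n = 12, paired and pooled power are 49% and 52% at a true difference of 0.25 (SD 0.5). At D = 0 they are 41% and 46% with SD 0.75, and 11% and 9% with SD 1.0.

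**The case against.** Several points on the other side have force.

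- **The near-100% figures need a test that 10.5.1 does not spell out.** This stands. A reader might infer that, followed as written, the plan would declare a much stronger methoxyflurane equipotent. The documents do not support that: the stated procedure does not test the margin and would usually show the difference (step 4). Nor do they say that a non-significant difference will be read as equipotency. The figures describe what the written hypothesis would be worth if tested.
- **Meeting the bound against one dose and failing it against the other is not an error.** This also stands. When the two doses differ in effect, a split is the correct result, and separate equivalence tests would give it too. The fault is only that the section does not say which comparison counts.
- **The sample size is right for what it states.** Agreed. A reader might infer that 10 is miscalculated, but it is not.
- **The dose labels may be a drafting slip.** Possibly. Correcting them either way leaves the one-sided bound.
- **The SAP can still deal with it.** Partly. Section 10.4 allows changes to the statistical plan until database lock, before allocation is revealed, so a correction can still be made blinded. The separate SAP is not among the documents, so its content is unknown. It is promised as further detail, whereas this correction has to change the protocol's stated hypotheses.
- **The three pilots in 6.1 make a 1.0-point gap less likely.** They do, although the size of difference that would trigger a change is not defined. They do not alter the hypotheses.
- **The overall test includes placebo, so it already serves roughly as a check of assay sensitivity.** Fair. No harm from the gate has been quantified here.

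**Conclusion.** The point holds. Section 10.5.1 contradicts itself on the comparator, and once that is reconciled its alternative is still a one-sided claim that does not show equipotency. Nothing in 1.3, 6.1, 10.1 or 10.4 supplies the missing rule. This is an error in the stated hypotheses, not merely missing detail, and it should be corrected before database lock.

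Its size is conditional on testing the written hypothesis one-sided at 0.025 with 12 subjects, SD of differences 0.5 and one dose named throughout. On those terms the alternative is almost certain to be met when methoxyflurane is 0.5 points or more stronger, where an equivalence test would pass at most 2.5% of the time (5% at one-sided 0.05). The comparator contradiction needs no percentage, because it follows from the wording alone. No view is taken on which fentanyl dose should be the comparator.

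**What to change.** 1. Reconcile 10.5.1 so that each null and alternative pair names the same fentanyl dose. The sponsor decides whether one comparison is primary or each dose has its own pair.
2. Make the bound two-sided: null |D| ≥ 0.5, alternative |D| < 0.5. Justify 0.5 as an equivalence margin. Conclude equipotency only if the mixed-model confidence interval lies within ±0.5. State alpha and, if both doses are tested, the multiplicity rule.
3. Restate 10.1 with the equivalence power and the conditions it depends on.

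Options rather than corrections are Holm for the two doses, freeing the equivalence comparison from the overall-test gate, and an interpolated matching fentanyl dose with its confidence interval. If Holm is used and the other dose is 0.5 points away, simulated power for the matching dose is about 77% (paired) or 84% (pooled) at one-sided 0.05, and about 60% or 72 to 73% at 0.025.

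The cost is wording in 10.1 and 10.5.1 at the planned 12 subjects, handled as a protocol amendment under 11.3, together with less favourable power. With a paired analysis at one-sided 0.025, 80% power would need 13 subjects even at a true difference of 0. Section 6.4.1 says: "Patients who withdraw or are withdrawn from the study after randomisation cannot be replaced". The primary analysis in 10.3 is per-protocol, so the rows for 10 completers in the working are relevant. If the true difference is not near 0, or the SD exceeds 0.5, the trial may be unable to conclude either way, and the protocol should say so.

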10.5.2 Safety analyses

The safety analyses population will include all subjects who completed all 4 treatments.

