6.2.4 Withdrawal Visit

If one participant experience very unpleasant or a severe adverse effect during a session, the session will be terminated. The participant will then be excluded from the rest of the study.

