6.3 Criteria for Patient Discontinuation

Subjects may be discontinued from study treatment and assessments at any time. Specific reasons for discontinuing a subject for this study are:

- Voluntary discontinuation by the patient who is at any time free to discontinue his/her participation in the study, without prejudice to further treatment.
- Safety reason as judged by the Principal Investigator
- Major protocol deviation
- Incorrect enrolment i.e., the patient does not meet the required inclusion/exclusion criteria for the study
- Patient lost to follow-up
- A female patient becoming pregnant
- Deterioration in the patient's condition which in the opinion of the Principal Investigator warrants study medication discontinuation (to be records as an AE or under Investigator Discretion)
- Patient's non-compliance to study treatment and/or procedures
- Serious adverse effects of any of the drugs

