8.5.4 Clinical Study Report

The adverse events and serious adverse events occurring during the study will be discussed in the safety evaluation part of the Clinical Study Report.

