10.3 Population for Analysis

The following populations will be considered for the analyses:

- The full analysis population: All randomized subjects having received at least one dose of study medication and where a minimum of data is collected.
- The per-protocol population: All randomized subjects completing the study without major protocol violations. Definition of major protocol violations will be specified in the statistical analysis plan, and the final criteria will be defined prior to database lock. Data concerning the primary endpoint should be collected.
- Safety population: Includes all randomized subjects who have received at least one dose of study medication. Subjects who withdraw from the study will be included in the safety analysis. A list of withdrawn subjects, preferably with the reasons for withdrawal, will be made.
- The primary statistical analysis will be based on the subjects meeting the definition of the protocol population according to inclusion and exclusion criteria and with no major protocol violations.
- The secondary analysis will include all patients receiving study treatment.

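### Section 10.5.2 restricts the safety population to volunteers who finish all four treatments, which contradicts 10.3 and removes those withdrawn for adverse effects in sessions 1 to 3

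*Combined protocol and SAP*

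**What the plan says.** The plan defines the safety population twice.

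- Section 10.3 (Population for Analysis), safety population: "Includes all randomized subjects who have received at least one dose of study medication". It continues: "Subjects who withdraw from the study will be included in the safety analysis". It also asks for a list of withdrawn subjects, with reasons where possible.
- Section 10.5.2 (Safety analyses), whose whole text is one sentence: "The safety analyses population will include all subjects who completed all 4 treatments".

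Three other sections determine who can fall between the two definitions.

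- Section 6.2.4 ends a session when an adverse effect is very unpleasant or severe, and then: "The participant will then be excluded from the rest of the study".
- Section 6.3 lists reasons for discontinuation. They include voluntary withdrawal, non-compliance, loss to follow-up and "Serious adverse effects of any of the drugs".
- Section 6.4.1 says "All patients randomized will be included in the study population", and also "Patients who withdraw or are withdrawn from the study after randomisation cannot be replaced".

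Section 10.4 leaves further detail to a separate SAP. It does not mention this conflict or say which section takes precedence.

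**The concern.** A safety population should be fixed by exposure: whoever was dosed is counted. Section 10.5.2 fixes it by completion, and in this trial completion depends partly on tolerability, because an adverse effect that ends a session also ends participation. Membership of the safety set would then depend on the outcome that the set is meant to describe, and the volunteers with the worst reactions would be the ones left out.

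The loss extends beyond the session in which the event occurred. A volunteer stopped in session 3 would also take away the safety data from sessions 1 and 2, which were collected on other treatments.

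This touches the reason for the trial. Sections 1.1 and 1.3 justify studying methoxyflurane on the ground that it lacks the hypotension and respiratory depression of opioids, and 1.3 plans to record side effects for both drugs. What is at stake is the counts and denominators in the safety summaries. The pain endpoints and the visibility of individual events are separate matters.

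**Working it through.** **Inputs.** 12 volunteers (section 4.2); four treatments each in randomised order (5.3); the withdrawal and no-replacement rules in 6.2.4, 6.3 and 6.4.1. The plan states no withdrawal rate and no expected adverse-event rate.

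**The plan's own figure.** The only related calculation is the sample size in 10.1: n = 10 for 80% power, difference 0.5, SD of differences 0.5, paired t-test, two-sided 0.05. The noncentral t distribution gives power 0.748 at n = 9 and 0.803 at n = 10, so the figure reproduces. It concerns pain scores and is the same under either safety definition. The increase to 12 is explained by blocking and not as an allowance for dropout.

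**Step 1: who is counted.**

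| Volunteer | 10.3 | 10.5.2 |
|---|---|---|
| Finishes all four sessions | counted | counted |
| Stopped for an adverse effect in sessions 1–3 | counted | dropped |
| Leaves in sessions 1–3 for another reason after a dose | counted | dropped |
| Dosed in session 4, session then terminated | counted | not defined |

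The second row follows from 6.2.4: a volunteer barred from later sessions cannot finish four treatments. The last row is open because the plan does not say whether a terminated session counts as a completed treatment.

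**Step 2: effect on an event rate.** Suppose k of 12 dosed volunteers have an event and exactly one of the k is dropped. The gap is k/12 − (k−1)/11.

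- k = 1: 1/12 − 0/11 = 8.3% − 0% = 8.3 points
- k = 4: 4/12 − 3/11 = 33.3% − 27.3% = 6.1 points
- k = 6: 6/12 − 5/11 = 50.0% − 45.5% = 4.5 points

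If every volunteer with the event is withdrawn for it in sessions 1–3, 10.5.2 always reports zero: 1/12, 2/12 and 3/12 (8.3%, 16.7%, 25.0%) become 0/11, 0/10 and 0/9.

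**Step 3: direction.** Let d volunteers with the event and e without it be dropped. The completer rate (k−d)/(12−d−e) is below k/12 exactly when d(12−k) > k·e, that is, when d/k > e/(12−k). The rate is understated when people with the event drop out more often than people without it. The rule in 6.2.4 pushes in that direction for events severe enough to end a session.

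**Step 4: how often the two sets would differ.** Assume a withdrawal risk p per session for any reason, equal across treatments and independent between sessions and volunteers. These are illustrations and not estimates. Over sessions 1–3 the chance that at least one of 12 is dropped is 1 − (1−p)^36, and the expected number is 12[1 − (1−p)^3]. If session 4 terminations also count as non-completion, the exponents become 48 and 4.

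| p | Sessions 1–3: chance of at least one | Expected | Sessions 1–4: chance of at least one | Expected |
|---|---|---|---|---|
| 1% | 30% | 0.4 | 38% | 0.5 |
| 2% | 52% | 0.7 | 62% | 0.9 |
| 5% | 84% | 1.7 | 91% | 2.2 |
| 10% | 98% | 3.3 | 99% | 4.1 |

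**The case against.** The strongest reply is that little depends on this sentence. Safety is not a listed endpoint, and 10.5.2 specifies no rate, comparison or test. Section 8.5.1 sends adverse events to the CRF, and 8.5.4 says those "occurring during the study will be discussed in the safety evaluation part of the Clinical Study Report". Section 10.3 also requires a list of withdrawn subjects, so with 12 volunteers a reader could see who is missing. If all 12 finish, the two definitions coincide. The 10.5.2 sentence does not contain the word only, and 10.3 is the dedicated and more explicit text. Dropping an event-free volunteer raises a rate instead of lowering it: 4/12 (33.3%) becomes 4/11 (36.4%). The withdrawal risks in the illustration have no source in the documents.

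Much of this is right, and it limits the claim. Individual events would not be hidden. Section 8.1.1 exempts mild expected opioid effects from recording, but an event that ends a session is outside that exemption. A single rate can move either way, and the assumed risks show only how easily the two sets could diverge.

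The conflict itself is not answered. A sentence defining a population by completion reads as a restriction; on the looser reading it defines nothing and still has to be squared with 10.3. A list of withdrawals does not put those people back into a table. The population must also be settled before anyone knows whether all 12 finish. The separate SAP, which was not available for this review, could settle the point, but the present text does not.

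**Conclusion.** The point holds. The plan contains two incompatible safety populations with no rule of precedence, and the one placed under the safety analysis heading selects on tolerability. If 10.5.2 is applied, volunteers withdrawn for adverse effects in sessions 1–3 are missing from the summaries whatever their true number, and event rates are expected to be understated for events that lead to withdrawal. The plainest case is 1/12 (8.3%) against 0/11 (0%), and the gap narrows for commoner events.

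The contradiction rests on the text alone and needs no assumed rate. The size of any distortion depends on withdrawals that the documents do not predict, and it is nil if everyone finishes. The primary and secondary pain analyses, the sample size and the reporting of individual events are unaffected. It should be corrected before database lock, because a rule in the plan gives a wrong result as written and the correction is very small.

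**What to change.** Replace the sentence in 10.5.2 with the 10.3 definition: all randomised subjects who received at least one dose, including those who withdraw and those whose session is terminated, session 4 included. That alone removes the contradiction and the session 4 ambiguity.

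As a useful addition for a crossover, state that events are summarised by the treatment received in each session, with the number dosed in that session as the denominator. The correction does not depend on this.

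The cost is one sentence in the protocol, carried into the separate SAP before database lock. No new data are needed, and no clinical procedure changes.
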